3.5 Follow Up

Patients will continue treatment until:

- Disease Progression
- Unacceptable toxicities
- Patient decision / withdrawal of consent
- Investigator decision

4 TRIAL TREATMENT

4.1 IMP Administration and Schedule

Trial treatment must begin with 28 days of study enrolment. 400mg of Itacitinib will be administered QD;

The IMP is produced in the USA but shipped to Catalent Bathgate in the UK for distribution, each bottle has 35 x 100mg tablets. Study drug will be labelled in accordance with Good Manufacturing Practice (GMP), local regulatory requirements and all other applicable laws and regulations and QP released for the EU directly by Calatent Bathgate. Supplies of Itacitinib will be stored appropriately at the study site in the hospital pharmacy, where dispensing will also take place. IB will be used as Reference Safety Information (RSI).

4.2 Dose Modifications

4.2.1 Dose Interruptions

Clinically indicated dose interruptions of JAK-I are permitted for up to 14 days. If a treatment break continues for greater than 14 days the patient will need to withdraw from study.

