2.2 Secondary Objectives and Endpoints

| Objective | Endpoint |
|---|--|
| To assess the efficacy of Itacitinib by progression free survival (PFS) | PFS, defined as time from study entry to first evidence of disease progression assessed by mRECIST v1.1 or death due to any cause. |
| To assess the efficacy of Itacitinib by overall survival (OS) | OS, defined as time from study entry to death due to any cause. |

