3.4 Procedures and Measurements

3.4.1 Visit Schedule

Patients will be seen at screening then on day 1 and day 7 of cycle 1 and then every 4 weeks (from date of day 1) in clinic whilst on treatment. Treatment will continue until disease progression. When the patients stops treatment they will be required to attend a safety follow-up visit 28 days of treatment completion. For assessment details see table 1.

Table 1: Scheduled assessments

| Time point → Assessment ↓ | Screening | Cycle 1 | | Cycle 2 | Cycle 3 | Cycle 4 | Cycle 5 | Cycle 6 - Onwards | End of Treatment ¹⁰ | Safety Follow-up |
|---|-----------------|-----------------|-----------------|---------|---------|---------|---------|-------------------------------|-----------------------------------|--------------------------------|
| | Day -28 to 0 | Day 1 Week 1 | Day 7 Week 1 | Week 4 | Week 8 | Week 12 | Week 16 | Week 20 – Every 4 Weeks | | 28 days after last dose. |
| Informed Consent | X | | | | | | | | | |
| Medical History | X | | | | | | | | | |
| Demographics | X | | | | | | | | | |
| Height | X | | | | | | | | | |
| Vital Signs ¹ | X | X | X | X | X | X | X | X | X | X |
| Physical Exam | X | X | X | X | X | X | X | X | X | X |
| ECOG Performance Status | X | X | X | X | X | X | X | X | X | X |
| ECG ⁶ | X | | | | x | | | X ⁷ | | |
| Pregnancy Test | X ¹¹ | | | X | X | X | X | X | | |
| Haematology ² | X | X | X | X | X | X | X | X | X | X |
| Biochemistry ³ | X | X | X | X | X | X | X | X | X | X |
| Serology ⁴ | X | | | | | | | | | |
| Tumour Assessments (mRECIST) ⁵ | X | | | | X | | | X ⁵ | X ⁹ | |
| Archival Tissue or Fresh Frozen Research Biopsy – Mandatory | X | | | | | | | | | |
| Research Bloods ⁸ | X | | | | X | | | X ⁸ | X | |
| ctDNA sample ⁸ | X | | | | X | | | X ⁸ | X | |
| PK Sample ⁶ | | | X | | | | | | | |
| Itacitinib administration | | X | | X | X | X | X | X | | |
| Adverse Events | | X | | | | | | | | |
| Concomitant Medications | | X | | | | | | | | |

- Vital signs include weight, blood pressure, pulse, temperature
- Haematology includes: white blood cell count (WBC) with differential, haemoglobin (Hgb), haematocrit (Hct), and platelet count
- Biochemistry includes: Chem 7 (sodium [Na], potassium [K] chloride [Cl], bicarbonate [CO₂], blood urea nitrogen [BUN], creatinine [Cr], glucose), liver function tests (LFTs - ALT, AST, alkaline phosphatase, total bilirubin, direct bilirubin), LDH, total protein, calcium, phosphate, magnesium, and cholesterol.

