- Serology includes: hepatitis B surface antigen, hepatitis B surface antigen antibody, hepatitis B core antibody, hepatitis C virus antibody, HCV-RNA load, HIV serology.
- CT Scans at baseline may be performed 28 days prior to study drug administration. Subsequent tumour assessments will occur every 8 weeks from first Itacitinib dose until progression or withdrawal.
- PK Samples only applicable for the first 10 patients and should be collected on day 7 prior to first dose of Itacitinib and at 1 hour, 2 hours and 4-8 hours post dose.
- ECG every 3 cycles from first Itacitinib dose until progression or withdrawal.
- Research Bloods & ctDNA to be collected every 8 weeks from first Itacitinib dose until progression or withdrawal.
- Tumour assessment only applicable if last measurement was more than 4 weeks.
- For all patients when they finish treatment, if this is at a cycle visit then end of treatment assessments are done in place of the cycle visit assessments.
- Serum test, 14 days before first study drug administration

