7.2.1 Analysis Plan

Due to sample size constraints, for the primary outcomes of assessing the safety and tolerability of Itacitinib and overall response rate, we will use descriptive measures such as frequencies and percentages.

All patients who receive at least one dose of study treatment will be included in the safety analysis set. The frequency of adverse events (AEs) will be assessed for severity (NCI CTCAE v4.03), expectedness, seriousness and causal relationship to study drugs(s). In addition, AEs will be summarised by toxicity type, impact on study drug(s) and by timing.

All efficacy data in the study will be analysed on an intention-to-treat (ITT) basis, regardless of treatment received. To be considered 'evaluable' for the primary efficacy analysis, a patient must have a week 8 tumour assessment or evidence of disease progression or death prior to week 8.

For quality of life measures, both means and standard deviations for continuous variables as well as frequencies and percentages for categorical variables will be used.

For the translational / exploratory endpoints, appropriate descriptive measures as well as univariate models will be shown as dependent on whether the relevant measure is categorical or continuous, whether the test is paired or not and whether is it normally or non-normally distributed as indicated below. Translational endpoints may not be included in the Clinical Study Report.

Univariate models will be performed for all demographic and other study variables, as statistically appropriate, as well as to test for confounding due to sample size constraints, with models such as Fisher's exact test or the Chi-square test utilised for categorical variables and t-tests or the Wilcoxon test (if the continuous variable does not follow a normal distribution) for continuous ones. For all estimates, 95% confidence intervals will be calculated.

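### Section 4.2.1 withdraws a patient from the study after a break of more than 14 days, which, read literally, ends scans before the week-8 response assessment in a patient who has not progressed

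*Combined protocol and SAP*

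**What the plan says.** - **Section 4.2.1 (Dose Interruptions)** allows clinically indicated breaks of up to 14 days, then adds: "If a treatment break continues for greater than 14 days the patient will need to withdraw from study".
- **Table 1, scan footnote (section 3.4.1):** "Subsequent tumour assessments will occur every 8 weeks from first Itacitinib dose until progression or withdrawal".
- **Table 1, End of Treatment column** marks a tumour assessment, with the footnote "Tumour assessment only applicable if last measurement was more than 4 weeks". End of Treatment assessments apply to all patients who finish treatment. The later safety visit, 28 days after the last dose, has no tumour assessment.
- **Section 3.5 (Follow Up)** opens with "Patients will continue treatment until" and lists reasons for stopping drug. It schedules no follow-up.
- **Section 4.2.3** is headed Study Withdrawal, but its text concerns withdrawal from study treatment only. It does not list the 14-day rule.
- **Section 7.2.1** defines who is evaluable for the response endpoint: "a patient must have a week 8 tumour assessment or evidence of disease progression or death prior to week 8". It also says: "All efficacy data in the study will be analysed on an intention-to-treat (ITT) basis, regardless of treatment received".
- **Section 2.2** gives the secondary endpoint as "PFS, defined as time from study entry to first evidence of disease progression assessed by mRECIST v1.1 or death due to any cause".

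**The concern.** The analysis asks for outcomes that the dosing rule can prevent from being collected. Under section 4.2.2, grade 3 or 4 toxicity means withholding drug until it settles to grade 1 or less. If that takes more than 14 days, 4.2.1 takes the patient out of the study, and the scan footnote then ends scheduled imaging. A patient who has progressed or died before week 8 is evaluable anyway. One who is stable or responding is not, unless a week-8 scan exists.

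Week-8 response is one of two primary outcomes and drives the two-stage stopping rule in section 7.1, which accrues exactly 15 + 10 = 25 patients and states no allowance for missing outcomes. Outcomes lost through 4.2.1 would often follow toxicity, so they are plausibly informative. The same literal reading cuts off PFS for these patients: it is defined by progression or death, not by stopping drug, and later progression would go unseen.

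**Working it through.** **1. Timing.** Take week 8 as day 57, that is 8 × 7 = 56 days after day 1. If the first missed dose is on day d, the 15th missed day is d + 14. The break therefore passes 14 days before the week-8 scan when d + 14 ≤ 56, so d ≤ 42.

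**2. What the End of Treatment scan recovers.** The documents do not fix the day of this visit. Assume that it falls on day d + 14, and let the baseline scan be on day s, between −28 and 0. The scan is waived when (d + 14) − s ≤ 28.

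- Baseline scan on day 0, dosing on days 1–7, first missed dose on day 8: the break passes 14 days on day 22. The last scan is 22 days old, so none is due and there is no post-baseline scan.
- Baseline scan on day −14, last dose on day 10, first missed dose on day 11: the break passes 14 days on day 25. The last scan is 25 + 14 = 39 days old, so one is due, at about week 4.
- Latest baseline (s = 0): the waiver applies only for d ≤ 14. For d from 15 to 42 a scan is due on days 29 to 56.

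So having no post-baseline scan at all needs a very early break and a recent baseline scan. Having a scan, but before week 8, is the wider case.

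**3. The plan's own design (section 7.1).** Inputs: p0 = 0.05, p1 = 0.25; stop if 0 of the first 15 respond; success if at least 4 of 25 respond. With a patients lost from stage 1 and b from stage 2, each counted as a non-responder:

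P(success) = Σ over x from 1 to 15 − a of Bin(x; 15 − a, p) × P(Bin(10 − b, p) ≥ 4 − x).

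With no loss at p = 0.25:
0.0668 × 0.4744 + 0.1559 × 0.7560 + 0.2252 × 0.9437 + 0.5387 = 0.901, where the last term is P(at least 4 of 15). This reproduces the stated 0.90. At p = 0.05 the result is 0.0336, within the stated 0.05.

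**4. One lost outcome, for illustration.** For a = 1, b = 0:
0.0832 × 0.4744 + 0.1802 × 0.7560 + 0.2402 × 0.9437 + 0.4787 = 0.881.

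| Case | Power at 25% | Type I error at 5% |
|---|---|---|
| No loss | 0.901 | 0.0336 |
| One lost in stage 1 | 0.881 | 0.0293 |
| One lost in stage 2 | 0.883 | 0.0295 |
| Each patient lost with probability 4% (p × 0.96) | 0.880 | 0.0295 |

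The chance of stopping at the interim when the true rate is 25% moves from 0.75^15 = 1.3% to 0.75^14 = 1.8% with one stage 1 loss.

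**5. Range.** If outcomes are lost at random and counted as non-response, power is 0.856 at 8%, 0.829 at 12%, 0.797 at 16% and 0.762 at 20%. These rates are assumptions; the documents give none.

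**The case against.** The strongest reply is that the scan footnote runs from first dose and ends at progression or withdrawal, not at end of treatment. If withdrawal means leaving the study, a patient who stops drug for toxicity and stays in the study is still due the week-8 scan. Section 8.3 leans the same way: patients moved to alternative treatment remain in follow-up and analysis. This stands for patients who stop for reasons other than the 14-day rule. It does not rescue the 14-day case, because 4.2.1 says study, and 8.3 covers clinician-chosen alternative treatment and names no scans.

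A reader might infer that no scan at all is required once treatment stops. The documents do not support that. The End of Treatment scan is required unless one was done within 4 weeks, and on one reading the 8-weekly scans continue off drug. The section 3.2 flowchart is also not visible in the text reviewed.

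Section 7.2.1 sets no window around week 8. On the assumption in step 2, breaks starting on days 29–42 give an End of Treatment scan on days 43–56, and an analyst might accept it as the week-8 assessment. That narrows the exposure, but leaves it to interpretation.

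The separate SAP promised in section 7.2 could say how a missing outcome is counted. It cannot supply a scan that was never done. Section 7.2 keeps all enrolled patients in the intention-to-treat analysis, so a lost scan need not shrink the denominator; it leaves that patient's response unknown.

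Finally, this is a 25-patient pilot whose primary outcomes are summarised descriptively, and the effect of one loss is modest. That is fair, and it argues for a wording change rather than a redesign.

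**Conclusion.** The point holds in a limited form. Following 4.2.1 and the scan footnote as written can lose the week-8 outcome of a patient who has not progressed and whose break passes 14 days before that scan. The End of Treatment scan reduces the loss but does not close it. For patients who stop drug for other reasons, whether scans continue depends on an undefined word, so absence of scans is not shown and neither is general loss of PFS follow-up.

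The size is illustrative: about 2 points of power per lost patient at first, from a design that has none to spare (0.901 against 0.90). This assumes that the lost patient would have responded at the full 25% and is counted as a non-responder. If that patient would not have responded, nothing is lost. An inference that the false-positive risk increases would be wrong under this counting, since type I error falls slightly. The change is worth making because it is cheap and protects a co-primary endpoint.

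**What to change.** 1. In section 4.2.1, replace withdrawal from the study with *permanently discontinue study treatment*. The 14-day dosing limit itself stays.
2. List the 14-day rule in section 4.2.3 among the reasons for stopping study treatment.
3. In the Table 1 scan footnote, define withdrawal as withdrawal of consent to study follow-up. The week-8 scan and the existing 8-weekly scans then continue until progression or death for patients who stop drug without progression.

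The cost is three wording changes and a few off-treatment scans and visits.

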4.2.2 Dose Reductions

Toxicities will be graded according to NCI-CTCAE version 4.03. Dose reductions are to be made according to the system showing the greatest degree of toxicity.

All patients will receive 400mg QD until the patient suffers from disease progression. Should any patients suffer from significant toxicity the dose can be reduced to 300mg QD.

| Toxicity | Grade 1 | Grade 2 | Grade 3 | Grade 4 |
|--------------------|---------------------------------|---------------------------------|---|---|
| Non-haematological | Continue at the same dose level | Continue at the same dose level | Withhold dose until toxicity is grade ≤ 1 , then resume treatment at the same dose level. If the patient experiences a second grade 3 toxicity, withhold dose until the toxicity is grade ≤ 1 , then reduce dose to 300mg QD and resume treatment. If there is no toxicity grade ≥ 1 after 28 days re-escalation to 400mg QD should be done for 28 days. Without further | Withhold dose until toxicity is grade ≤ 1 , resume treatment at reduced dose level of 300mg QD or discontinue at the discretion of the principal investigator. |

| | | | | |
|----------------|---------------------------------|---------------------------------|---|---|
| | | | aggravation of toxicity full dose can be continued. Generally the dose with toxicity grade ≤ 1 should be maintained. | |
| Haematological | Continue at the same dose level | Continue at the same dose level | Withhold dose until toxicity is grade ≤ 1 , then resume treatment at the same dose level. If the patient experiences a second grade 3 toxicity, withhold dose until the toxicity is grade ≤ 1 , then reduce dose to 300mg QD and resume treatment. If there is no toxicity grade ≥ 1 after 28 days re-escalation to 400mg QD should be done for 28 days. Without further aggravation of toxicity full dose can be continued. Generally the dose with toxicity grade ≤ 1 should be maintained. | Withhold dose until toxicity is grade ≤ 1 , resume treatment at reduced dose level of 300mg QD or discontinue at the discretion of the principal investigator. |

4.2.3 Study Withdrawal

A subject **must** be withdrawn from **study treatment** IF:

- The subject has experienced an unacceptable toxicity
- The subject is unwilling to continue receiving study treatment.
- The subject has experienced clinical deterioration/disease progression.
- In the opinion of the investigator, it is in the best interest of the subject not to continue receiving the study treatment.
- The subject becomes pregnant.
- Consent to receive treatment is withdrawn.
- Termination of the study by the sponsor.
- Termination of the study by the local health authority, IRB, or IEC.

A subject **may** be withdrawn from **study treatment** if, during the course of the study:

- Is found not to have met eligibility criteria; the subject would be withdrawn if the investigator, determines that the subject would not benefit from participation in the study due to the eligibility deviation.
- Is noncompliant with study procedures or study drug administration in the opinion of the investigator.

5. CONCOMITANT MEDICATIONS AND MEASURES

All concomitant medications and treatments must be recorded in the CRF. Any prior medication received up to 28 days before randomization will be recorded in the CRF. Concomitant treatments and/or procedures that are required to manage a subject's medical condition during the study will also be recorded in the CRF.

5.1. Restricted Medications and Measures

- Inducers of CYP3A4 (Appendix A) may be used with caution, and investigators should seek other options if available.
 - Use of potent inhibitors of CYP3A4 (ketoconazole, clarithromycin, itraconazole, nefazodone or telithromycin, voriconazole or posaconazole, see Appendix A) and use of fluconazole should be avoided. If used, the itacitinib dose should be reduced from QID to BD with frequent complete blood count monitoring during the period of co-administration. Based on the low overall bioavailability of topical ketoconazole, there are no restrictions on topical ketoconazole in the study.
 - Moderate CYP3A4 inhibitors (Appendix A) may be used with caution. Differences in individual sensitivity and variation in potency of inhibition of various CYP enzymes may result in the need for a reduced dose of itacitinib during a period of concomitant medication use. If used, the itacitinib dose may be reduced from QID to BD with frequent complete blood count monitoring during the period of co-administration.
- Systemic corticosteroid doses greater than the equivalent of 10 mg/day prednisolone are not permitted from the screening visit through the follow-up visit.

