3.1 Design

This is a single arm phase Ib study to evaluate the effect of Itacitinib (a JAK1 inhibitor) in ~25 patients with advanced HCC. Eligible patients will receive Itacitinib every 400mg QD until disease progression, unacceptable toxicities or withdrawal of consent.

The first 10 patients will undergo attenuated pharmacokinetic profiling in cycle 1.

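### Section 5.1 lowers itacitinib for CYP3A4 inhibitors from a four-times-daily schedule that no patient follows, and gives no mg dose, so the rule cannot be carried out

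*Combined protocol and SAP*

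**What the plan says.** The regimen is stated consistently. Section 3.1: "Eligible patients will receive Itacitinib every 400mg QD until disease progression, unacceptable toxicities or withdrawal of consent". Section 4.1: "400mg of Itacitinib will be administered QD", supplied so that "each bottle has 35 x 100mg tablets". Section 4.2.2 repeats 400 mg QD and allows one lower level, 300 mg QD, for toxicity.

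Section 5.1 deals with CYP3A4 inhibitors in two items:

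- **Potent inhibitors and fluconazole.** These are discouraged; for example, "use of fluconazole should be avoided". If one is given anyway: "If used, the itacitinib dose should be reduced from QID to BD with frequent complete blood count monitoring during the period of co-administration".
- **Moderate inhibitors.** These are allowed with caution. The text says that individual differences "may result in the need for a reduced dose of itacitinib" while the other drug is taken, and that "the itacitinib dose may be reduced from QID to BD", again with frequent blood counts.

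Neither item states an amount in mg. Appendix A lists inhibitors and inducers by strength but gives no itacitinib dose.

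**The concern.** A dose-reduction rule has to start from the dose the patient is taking. This one starts from four intakes a day and ends at two, while patients take one. A pharmacist asked to apply it to someone on 400 mg QD has nothing to reduce from and no mg target to reduce to.

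Safety and tolerability is a primary objective (section 2.1), and these two sentences are the only dosing instruction for a CYP3A4 interaction. Moderate inhibitors are expressly permitted, and Appendix A counts common drugs such as diltiazem, verapamil, erythromycin and ciprofloxacin among them, so the situation could plausibly arise. Sites that meet it may choose different doses, and adverse events in those patients would then reflect different, unplanned dose levels.

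**Working it through.** The plan gives no figure to reproduce. The check sets the dosing statements side by side and then tests whether any reading of section 5.1 yields a single dose.

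**Inputs**

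| Item | Value | Source |
|---|---|---|
| Starting regimen | 400 mg QD | 3.1, 4.1, 4.2.2 |
| Only lower level, tied to toxicity | 300 mg QD | 4.2.2 |
| Tablet strength | 100 mg | 4.1 |
| Change with potent inhibitor or fluconazole | QID to BD, expected, no mg | 5.1 |
| Change with moderate inhibitor | QID to BD, optional, no mg | 5.1 |

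No QID regimen of itacitinib appears anywhere in the documents. Twice-daily schedules appear only in the accounts of other itacitinib studies in section 1.2.3.

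**Possible readings for a patient on 400 mg QD**

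1. *Literal.* Cannot be applied, because the patient is not on QID.
2. *QID is a slip for QD, with the same amount per intake.* 400 mg × 2 = 800 mg/day. This doubles the dose and contradicts the instruction to reduce.
3. *The intended change was BD to QD.* The patient is already on QD, so nothing changes.
4. *Same daily total, split in two.* 200 mg × 2 = 400 mg/day. No reduction.
5. *The proportional cut from four intakes to two.* 400 mg × 2/4 = 200 mg/day, or two tablets.
6. *Borrow the toxicity level.* 300 mg/day, which is 300/400 = 75% of the starting dose.
7. *Any other whole-tablet reduction.* 100 mg/day also satisfies the instruction.

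Readings 5, 6 and 7 all reduce the dose and can be made from whole tablets. The text does not choose among them.

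**For a patient on 300 mg QD**

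The proportional cut is 300 mg × 2/4 = 150 mg, or 1.5 tablets, which whole 100 mg tablets cannot provide. The whole-tablet daily doses below 300 mg are 100 mg (100/300 = 33%) and 200 mg (200/300 = 67%). This case is narrower: the section 4.2.2 table reaches 300 mg QD only after a second grade 3 toxicity or after a grade 4 toxicity.

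**Interaction with section 4.2.2**

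The grade 3 entries tell sites to go back to 400 mg QD when a patient reduced to 300 mg has been free of toxicity for 28 days. They make no exception for a patient still taking an inhibitor. A site that borrowed the 300 mg level for an interaction could find this rule pointing it back to full dose while the inhibitor continues.

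**The case against.** The best case on the other side is that the consequence is small and safeguards exist.

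- The sentence that expects a reduction applies only when a drug that should be avoided is used anyway.
- The moderate-inhibitor sentence is discretionary and appeals to individual sensitivity, so some variation between investigators is intended.
- Blood counts are taken frequently during co-administration, and haematology is scheduled at every visit in Table 1.
- Section 4.2.1 offers a hold: "Clinically indicated dose interruptions of JAK-I are permitted for up to 14 days". That can cover a short antibiotic or antifungal course.
- Section 4.2.2 withholds drug at grade 3 or 4 and allows discontinuation at grade 4.
- Section 4.2.3 requires withdrawal from treatment when the investigator judges that best for the patient.
- Section 8.3 lets the clinician depart from protocol treatment at any stage, with reasons recorded.
- Both sentences tie the reduction to the time the two drugs are given together, so its duration is broadly stated.

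All of this stands, and it limits the seriousness. None of it supplies a dose. Holding, withdrawing and departing from protocol are alternatives to the rule, and a break longer than 14 days means leaving the study. The toxicity table acts after harm has appeared, whereas the section 5.1 reduction is meant to apply without waiting for it.

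One could also say that the investigator brochure may contain the dose. It is not among the documents reviewed, section 5.1 does not refer to it for this purpose, and a dose given there would not correct the protocol wording.

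A reader might go further and infer three things that the documents do not support:

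- *That sites will double the dose to 800 mg/day.* That reading contradicts the instruction to reduce and is unlikely. Section 1.2.3 reports repeated dosing up to 600 mg twice daily (1200 mg/day) in healthy adults, but describes no inhibitor use, so it shows neither harm nor safety here.
- *That the ambiguity has a definite fold-size.* Admitting 200 and 300 mg/day gives 300/200 = 1.5; adding 100 mg/day gives 300/100 = 3. The ratio depends on which readings are admitted and is not a property of the text.
- *That the Appendix A ratios show how far itacitinib exposure would rise.* They are for other substrates, such as midazolam; none is for itacitinib.

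**Conclusion.** The inconsistency is certain. Both CYP3A4-inhibitor sentences in section 5.1 start from a schedule that does not exist in this trial, and no simple correction of the abbreviation rescues them. The instruction cannot be carried out, and the intended dose cannot be determined from these documents.

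The size of the consequence is limited and cannot be put into numbers. The documents give neither an expected number of inhibitor users nor any interaction data for itacitinib, so no exposure increase, number of patients affected or fold-spread is claimed. No effect on the response-rate endpoint, the sample size or the Simon two-stage design has been shown.

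The point should be fixed because this is the only interaction-dose rule in a trial with safety as a primary objective, and the correction is cheap. The conclusion assumes only that the regimen in sections 3.1, 4.1 and 4.2.2 is the intended one, as their agreement indicates.

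**What to change.** 1. In both section 5.1 sentences, replace the QID-to-BD phrase with an explicit once-daily dose in mg, in multiples of the 100 mg tablet and below the patient's current level. State it for each starting level, 400 mg QD and 300 mg QD.
2. Keep the present strength of each instruction: expected for potent inhibitors and fluconazole, optional for moderate inhibitors. Set separate doses for the two groups if the sponsor's clinical pharmacology supports that.
3. The sponsor must supply or confirm every figure. From 400 mg QD, 200 mg QD is a candidate only: it comes from the halving suggested by four intakes becoming two, which is the phrase in error. From 300 mg QD, the documents do not decide between 100 and 200 mg QD.
4. State plainly that the reduced dose applies for as long as the inhibitor is co-administered.
5. Add to section 4.2.2 that the 28-day return to 400 mg QD does not apply while the inhibitor continues.

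The cost is a short protocol amendment, a notice to sites, and whatever regulatory and ethics notification that requires. No new tablet strength is needed, and the sample size and two-stage design are unchanged.
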